9.1.2.2 Full Physical Exam

The investigator or qualified designee will perform a complete physical exam during the screening period. Clinically significant abnormal findings should be recorded as medical history. A full physical exam should be performed during screening and during all on treatment and FU visit as reported in the Trial Flow Chart. For cycles that do not require a full physical exam per the Trial Flow Chart, the investigator or qualified designee will perform a directed physical exam as clinically indicated prior to trial treatment administration.

9.1.2.3 Vital Signs

The investigator or qualified designee will take vital signs at screening, prior to the administration of each dose of trial treatment and at treatment discontinuation as specified in the Trial Flow Chart (section 8.0). Vital signs should include temperature, pulse, respiratory rate, weight and blood pressure. Height will be measured at screening only.

9.1.2.4 ECG

The investigator or qualified designee will perform a 12-lead ECG.

9.1.2.5 Eastern Cooperative Oncology Group (ECOG) Performance Scale

The investigator or qualified designee will assess ECOG status (see Appendix 1) at screening, prior to the administration of each dose of trial treatment and discontinuation of trial treatment as specified in the Trial Flow Chart (section 8.0).

9.1.3 Tumor Imaging and Assessment of Disease

9.1.3.1 Tumor Imaging

Tumour imaging will be performed at each center by local radiologists according to RECIST and to iRECIST (see appendix 4). However CT-Scans will be cloud stored for post-trial centralized response revision.

Tumor imaging is strongly preferred to be acquired by computed tomography (CT). For the abdomen and pelvis, contrast-enhanced magnetic resonance imaging (MRI) may be used when CT with iodinated contrast is contraindicated, or when local practice mandates it. MRI is the strongly preferred modality for imaging the brain. The same imaging technique regarding modality, ideally the same scanner, and the use of contrast should be used in a participant throughout the study to optimize the reproducibility of the assessment of existing and new tumor burden and improve the accuracy of the assessment of response or progression based on imaging.

Imaging assessment will be as follow:

- **SCREENING Phase:** CT scans performed up to 28 days prior to screening eligibility check are considered valid.
- **PRIMING Phase:** RECIST 1.1 will be used to assess response to TMZ. Patients in CR/PR/SD are reassessed every 8 weeks. However, in order to fulfil RECIST, the FIRST occurrence of CR/PR MUST be reconfirmed not earlier than 4 and not later than 5 weeks later.
- **TRIAL Phase:** Tumor imaging must be performed within 0 to 28 days prior to starting treatment with pembrolizumab. Local reading (Investigator assessment with site radiology reading) will be used to determine eligibility.
 - Baseline for D-cohort patient; Imaging data from Screening phase can be used, provided timeframe is less than 28 days.
 - Baseline for P-cohort patients: the baseline correspond to the TMZ PD imaging assessment.
 - During trial for both cohorts: tumor assessment must be performed every 9 weeks. However in order to fulfil RECIST, the FIRST occurrence of CR/PR MUST be reconfirmed not earlier than 4 and not later than 5 weeks later.
 - At RECIST PD clinically stable patients should not undergo treatment discontinuation until progression is confirmed locally 4 to 8 weeks later according to iRECIST (see Table 9.1.3 and Figure 9.1.3).

Participants who have unconfirmed disease progression may continue on treatment at the discretion of the Investigator until progression is confirmed by the site provided they are clinically stable. Participants who receive confirmatory imaging do not need to undergo the next scheduled tumor imaging if it is less than 4 weeks later; tumor imaging may resume at the subsequent scheduled imaging time point, if clinically stable. Participants who have confirmed disease progression by iRECIST, as assessed by the site, will discontinue study treatment.

- In participants who discontinue study treatment, tumor imaging should be performed at the time of treatment discontinuation (± 4 -week window). If previous imaging was obtained within 4 weeks prior to the date of discontinuation, then imaging at treatment discontinuation is not mandatory. In participants who discontinue study treatment due to documented disease progression, this is the final required tumor imaging.
- In case of discontinuation of treatment for any reason other than disease progression, patients will still be re-evaluated every 8 weeks until disease progression or start of a new treatment or death or patients refusal, whichever comes first.
- After 1 year, the imaging time point will occur approximately every 12 weeks.
- At trial end, all in-Trial tumor assessments radioimaging data will be reviewed centrally by two radiologists who will read the CT/MRI scans blinded using the Quibim Precision[®] software to collect, store, and guide the revision of the imaging results. The imaging review protocol and tumor assessment reconciliation report will be included in the final study report and or in the publication of the study.

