5.4 Primary Endpoint

Objective response rate (ORR) to pembrolizumab in cohort P according to RECIST (as specified in table 9.1.3).

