9.1.3.2 Disease assessment

RECIST 1.1 (referencing a maximum of 5 target lesions in total and 2 per organ) will be used as a primary measure for assessment of tumor response and as date of disease progression.

The Sponsor might also require, for research purpose, to enable a broader sampling of tumor burden to be conducted centrally.

RECIST 1.1 Progression (PD) definition will be used for discontinuation of study treatment during the temozolomide PRIMING phase, and in TRIAL phase whenever the Investigator at site decide NOT to use iRECIST criteria, as described below. iRECIST is based on RECIST 1.1, but adapted to account for the unique tumor response seen with immunotherapeutic drugs.

Disease assessment in the TRIAL phase for both Cohorts takes into account the observation that some patients treated with immunotherapy can have a transient tumor flare, which might be misconstrued for PD by RECISTs, in the first few months after the start of pembrolizumab, and then experience subsequent disease response. Thus in the TRIAL phase, when tumor imaging shows PD by RECIST 1.1 the local investigator will re-assess the patient per iRECIST criteria according to the flow-chart in figure 9.1.3, table 9.1.3.

Per iRECIST, disease progression should be confirmed by the site 4 to 8 weeks after first radiologic evidence of RECIST 1.1 PD in clinically stable participants. Participants who have unconfirmed disease progression may continue on treatment at the discretion of the Investigator until progression is confirmed provided they have met the conditions detailed in Table 9.1.3 below.

Patients who receive confirmatory imaging do not need to undergo the next scheduled tumor imaging if it is less than 4 weeks later; tumor imaging may resume at the subsequent scheduled imaging time point, if clinically stable. Participants who have confirmed disease progression by iRECIST, as assessed by the site, will discontinue study treatment. Exceptions are detailed in table 9.1.3.

[figure not shown]
A description of the adaptations and iRECIST process is provided in Appendix 4, with additional detail in the iRECIST publication (Seymour et al., 2017).

Table 9.1.3: Imaging and Treatment after First Radiologic Evidence of Progressive Disease

	Clinically Stable		Clinically Unstable	
	Imaging	Treatment	Imaging	Treatment
Imaging and treatment options at first RECIST PD determination				

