10.2 Sample size calculation

A two-stage Green-Dahlberg design has been used [Green SJ and Dahlberg S Statistics in Medicine 11:853-862,1992], to calculate the sample size for the **P-cohort** under the following assumptions:

- The null hypothesis that the true (H_0) response rate is 10% (not considered clinically compelling) will be tested against a one-sided alternative (H_1).
- In the first stage, 10 patients will be accrued. If no responses are observed, the study will be stopped. Otherwise, 10 additional patients will be accrued for a total of 20.
- The null hypothesis will be rejected if 5 or more responses are observed in 20 patients.
- This design yields a type I error rate of .05, and power of 90% when the true response rate is 40%.
- In order to recruit 20 patients in the P-cohort the number of MMR unselected patients to be pre-screened for MMR status MGMT promoter methylation and the number of MGMT-PM+ to be primed with TMZ are reported in Table 10.1. below as well as in Study Diagram, section 4.2.

Table 10.1 Number of patients required in each trial Phase.

Number of Patients to be:	N	Expected Percent
RAS mut MMR proficient cases to be screened	670	A
expected MGMT IHC negative	335	B = 50% of A
expected promoter methylated in tissue	67	C=20% of B and 10% of A
expected with increase of mutational load ≥ 20 mutations/Mb (PRIMING Phase)	20	D= 30% of C

For cohort D, a precise sample size has NOT been calculated since the ORR in deficient patients is a secondary objective of the trial. We will enroll up to 34 MMR-D cases according to an estimated prevalence of 4-5 %. These patients will constitute the **D-cohort**. We expect a response rate between 40% (95% C.I. .18-.71) and 33% (95% C.I. .21-.46) as reported by Le et al., (2015 & 2019) with 11-14 responses accordingly.

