10.3.2 Primary analysis

The main analysis will focus on the objective response rate (ORR) of the P Cohort.

An objective response is defined as either a CR or PR assessed, as outlined in sections 9.1.3 and 10.3.1 (iEE population), first by RECIST 1.1 and then by iRECIST criteria at the discretion of the local Investigator.

Best objective response of either type will be centrally confirmed using the [Quibim Precision[®]](#) software (the cloud-based repository for radioimaging). In case of disagreement between local and central evaluation, the central response evaluation will be used for the analysis. The duration of response will be calculated accordingly.

An estimate of ORR and its 95% CIs will be calculated using the Clopper-Pearson method. Discrepant results, impinging in the acceptance of rejection of the null hypothesis, will be discussed and agreed upon between the Protocol Chair and the Sponsor.

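### Read literally, the 4-to-5-week reconfirmation rule leaves out lasting responses first reconfirmed later, and its upper limit serves no purpose in the primary ORR

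*Combined protocol and SAP*

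**What the plan says.** Section 9.1.3.1 (Tumor Imaging), TRIAL Phase, sets the routine schedule: "During trial for both cohorts: tumor assessment must be performed every 9 weeks". It then adds, as a condition for meeting RECIST, that "the FIRST occurrence of CR/PR MUST be reconfirmed not earlier than 4 and not later than 5 weeks later". The same sentence appears for the PRIMING Phase, where it does not bear on the primary endpoint.

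Section 5.4 gives the primary endpoint: "Objective response rate (ORR) to pembrolizumab in cohort P according to RECIST (as specified in table 9.1.3"). The table cited there deals with imaging and treatment after first progression and has no rule for confirming a response. Section 10.3.2 supplies the analysis definition: "An objective response is defined as either a CR or PR assessed, as outlined in sections 9.1.3 and 10.3.1 (iEE population"). That section puts RECIST 1.1 ahead of iRECIST and does not repeat the reconfirmation interval. On central review it says: "In case of disagreement between local and central evaluation, the central response evaluation will be used for the analysis". Section 9.1.3.1 refers to an imaging review protocol for that reading, which is not part of the documents.

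For progression, section 9.1.3.2 says that under iRECIST "disease progression should be confirmed by the site 4 to 8 weeks after first radiologic evidence of RECIST 1.1 PD". Table 9.1.3 and Appendix 4 let the repeat scan for persistent unconfirmed progression fall at the next scheduled visit.

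**The concern.** A minimum interval between first response and confirmation has a clear purpose: it screens out transient or misread responses. A maximum has no such purpose. A response still present at 9 weeks is better evidence of activity than one seen only at 4 to 5 weeks, yet on the literal wording it fails and the shorter one passes.

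The primary decision rests on a count of 5 in 20, so the definition of a countable response matters. If the limit is applied, true responders can be lost to scheduling. If it is not, whether a late-confirmed patient counts would be settled once open-label results are known. Section 10.3.2 already leaves discrepant results that affect the null hypothesis to agreement between the Protocol Chair and the Sponsor.

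**Working it through.** **Does the schedule make a miss possible?**
- The window is 4 to 5 weeks, that is days 28 to 35 after the first CR or PR.
- Routine TRIAL Phase scans are 9 weeks apart, so the next one falls 9 − 5 = 4 weeks after the window closes.
- The flow chart (section 8.0) lists tumor imaging every 9 weeks in the TRIAL Phase and shows no response-confirmation scan.
- Pembrolizumab is given every 3 weeks, with 3 days allowed either side (section 7.3.2). For a scan taken on a dosing day, the next visits fall on days 21 ± 3 = 18 to 24 and 42 ± 3 = 39 to 45. Neither overlaps days 28 to 35, so a separate attendance is needed.
- After treatment stops for reasons other than progression, scans are every 8 and later every 12 weeks. Both fall outside the window.

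**The plan's own figures.** Section 10.2 says the true "response rate is 10% (not considered clinically compelling) will be tested against a one-sided alternative". For stage 1 it says: "In the first stage, 10 patients will be accrued. If no responses are observed, the study will be stopped". Otherwise 10 more patients are accrued, and the null is rejected with 5 or more responses in 20. The stated type I error is 0.05, with power of 90% at a true rate of 40%.

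For response rate p, the exact probability of rejection is

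P(reject) = Σ (x = 1 to 10) of C(10, x) p^x (1 − p)^(10 − x) × P(Y ≥ max(0, 5 − x)), with Y ~ Binomial(10, p).

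- At p = 0.10 this is 0.0426.
- At p = 0.40 it is 0.9468. As a check, the single-stage probability of 5 or more in 20 is 0.9490. Removing the stage 1 stop gives 0.9490 − 0.6^10 × P(Y ≥ 5) = 0.9490 − 0.0060 × 0.3669 = 0.9468.

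The exact values do not equal 0.05 and 90%, but both lie on the favourable side, so the stated figures read as nominal bounds. That is a separate, minor matter.

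**Effect of losing late-confirmed responses.** Let m be the share of true responses not reconfirmed inside the window, each counted as a non-response. The counted rate is then p(1 − m). The documents give no value for m, so the range below is an assumption.

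| m | Counted rate at true 40% | Power | Stage 1 stop at true 40% | Type I error (true 10%) |
|---|---|---|---|---|
| 0 | 0.40 | 0.947 | 0.006 | 0.043 |
| 5% | 0.38 | 0.925 | 0.008 | 0.035 |
| 10% | 0.36 | 0.896 | 0.012 | 0.029 |
| 20% | 0.32 | 0.813 | 0.021 | 0.018 |
| 30% | 0.28 | 0.694 | 0.037 | 0.011 |

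Power falls below 0.90 at about m = 9.4% and below 0.80 at about m = 21%. Type I error falls throughout, so the effect runs one way, toward missing activity.

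**The case against.** **It may be only a scan instruction.** The sentence sits in an imaging section, and section 10.3.2 does not repeat it. The reference to section 9.1.3 could point only to the choice between RECIST 1.1 and iRECIST. A reader might infer that the plan expressly classes a late-confirmed response as a non-response. It does not. Still, the rule is capitalised as mandatory and tied to meeting RECIST, which is the endpoint's criterion, and no exception is given. The literal reading is the natural one.

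**Central review decides.** The central reading overrides the local one under a protocol that cannot be seen here. It may or may not apply the 5-week limit. This stands as a limit on what can be concluded.

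**The loss may be small.** The confirmation scan is mandatory and triggered by the response, so large miss rates are not self-evident. The calculation also treats every miss as permanent. Up to roughly 10% missed, the design keeps about its stated power. This stands.

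**One lost responder rarely decides.** Losing one response reverses the conclusion only if exactly 5 of 20 would otherwise respond. At a true 40% the single-stage probability of that is C(20, 5) × 0.4^5 × 0.6^15 ≈ 0.075. This also stands.

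**The progression window is not a true parallel.** It too has an upper limit, at 8 weeks, and it serves treatment decisions after possible tumor flare. The difference between the two windows is not in itself an error, and the point does not depend on it.

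**A strict rule is conservative.** It cannot create a false claim of activity. That is correct, but the cost falls on power, in a trial that plans to screen 670 patients to obtain 20.

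**Conclusion.** The point holds as a defect in a stated rule. Followed literally, the 5-week maximum excludes lasting responses that are reconfirmed late, including at the next routine scan. It adds no protection against false responses beyond the 4-week minimum.

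The size of the effect cannot be fixed from the documents. Under the assumed range at a true 40%, power goes from 0.947 with none missed to 0.896 at 10% and 0.694 at 30%, while type I error falls from 0.043 to 0.018 at 20% missed. These figures assume that missed confirmations are lost for good and that the central reading applies the same limit.

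Two stronger inferences are not supported. One is that the trial is underpowered because of this rule: no document gives a miss rate, and power stays near 90% up to about 10% missed. The other is a power loss worked out at a true 33%: that figure is an expected rate for cohort D (section 10.2), whereas cohort P's alternative is 40%.

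**What to change.** In section 9.1.3.1, and by reference in section 10.3.2, define a confirmed response for the ORR analysis as a CR or PR that persists on any scan at least 4 weeks after first documentation, with no upper limit, so that the next scheduled scan can confirm. Keep 4 to 5 weeks as the target date for the extra scan. Put the same definition in the central imaging review protocol, before the central reading starts.

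The cost is one sentence in each of the two sections and matching text in the review protocol, with no extra scans. The downside is a slightly higher counted response rate than under the strict window. Taking the 10% null as the rate of responses confirmed at any time from 4 weeks on, type I error stays at or below the design's exact 0.043.

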4.1.2 PRIMING Phase

MMR-P patients who have failed standard therapies including fluoropyrimidines, oxaliplatin, irinotecan plus or minus antiangiogenic agents (Bevacizumab, Regorafenib, others), showing negative MGMT protein in tissues and high levels of MGMT promoter methylation in tissue, will undergo a tumor biopsy (non-mandatory for the enrollment) to retrospectively determine the mutational load of their tumor (Baseline Mutational Load = B-ML), and will then receive TMZ therapy (OS dx5,q28 days) until progression.

At PD patients will be re-biopsied (mandatory for the enrolment) to prospectively determine the tumor mutational load (Post Temozolomide Mutational Load= TMZ-ML). Patients with a mutational load < 20 mutations/megabase will go off-study. Patients with a mutational load ≥ 20 mutations/megabase, will proceed to trial phase no longer than week 5 post TMZ-ML. This time gap is related to the technical time requirements to perform and interpret the mutational load assay.

During the 5-week gap, standard palliative treatment with the exception of regorafenib, can be delivered, at physician discretion, for symptomatic disease control.

Two liquid biopsies for the experimental NGS determination of the mutational load in plasma will also be performed concomitantly with the tissue biopsies: before treatment with TMZ (LB-B-ML) and at PD following TMZ treatment (LB-TMZ-ML).

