7.6.1 Acceptable Concomitant Medications

Throughout the study, investigators may prescribe any concomitant medications or treatments deemed necessary to provide adequate supportive care.

Anticancer therapy (chemotherapy, biologic or radiation therapy, palliative radiotherapy covering > 25% of the bone marrow reserve, and surgery) must not be given to patients during the study treatment, except to TMZ during TMZ Priming Phase.

Radiotherapy for palliation in non-target lesions with antalgic aim is allowed. Recombinant human granulocyte colony stimulating factor (G-CSF) or erythropoiesis stimulating agent use according to the current approved label or institutional guidelines is permitted.

All treatments that the investigator considers necessary for a participant's welfare may be administered at the discretion of the investigator in keeping with the community standards of medical care including palliative treatment (with the exception of regorafenib), delivered for symptomatic disease during the 5-week gap between progression to TMZ and start of pembrolizumab treatment (see 4.1.2).. All concomitant medication will be recorded on the case report form (CRF) including all prescription, over-the-counter (OTC), herbal supplements, and IV medications and fluids. If changes occur during the trial period, documentation of drug dosage, frequency, route, and date may also be included on the CRF.

All concomitant medications received within 28 days before the first dose of trial treatment and 30 days after the last dose of trial treatment should be recorded. Concomitant medications administered after 30 days after the last dose of trial treatment should be recorded for SAEs and ECIs as defined in section 9.2.

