8.0 TRIAL FLOW CHART

Trial Period:	SCREENING Phase	PRIMING Phase		TRIAL Phase		End of Treatment	Post-Treatment		
Treatment Cycle/Title:	Baseline Screening Phase (Visit 1)	TMZ Cycle 1 Day 1 and 5	Cycle \geq 2 Day 1 and 5	Pembro Cycle 1 Day 1 Q3	Cycle \geq 2 Day 1 Q3 week	Discontinuation	Safety Follow-up Visit (7)	Follow Up Visits (8)	Survival Follow-Up
Scheduling Window (Days):	Up to 28 days before Start of priming phase	treatment day 1, before drug administration	At time of Discontinuation	30 days post discontinuation	Every 8 weeks post discontinuation	Every 12 weeks			
Administrative Procedures									
SCREENING Phase Informed Consent	X								
PRIMING Phase Informed Consent		X							
TRIAL Phase Informed Consent				X					
Inclusion/Exclusion Criteria	X	X		X					
Demographics and Medical History	X								
Clinical Procedures/Assessments									
Prior and Concomitant Medication Review		X	X	X	X	X	X	X	
Post-study anticancer therapy status							X	X	
Survival Status									X
Treatment Administration (Temozolomide)		X ₁	X ₁						
Treatment Administration (Pembrolizumab)				X	X				
Review Adverse Events		X	X		X	X	X		
Full Physical Examination		X	X	X	X	X	X	X	
Vital Signs, Height and Weight		X	X	X	X	X	X	X	
ECG		X		X					
ECOG Performance Status		X	X	X	X	X	X	X	

Trial Period:	SCREENING Phase	PRIMING Phase		TRIAL Phase		End of Treatment	Post-Treatment		
Treatment Cycle/Title:	Baseline Screening Phase (Visit 1)	TMZ Cycle 1 Day 1 and 5	Cycle ≥ 2 Day 1 and 5	Pembro Cycle 1 Day 1 Q3	Cycle ≥ 2 Day 1 Q3 week	Discontinuation	Safety Follow-up Visit (7)	Follow Up Visits (8)	Survival Follow-Up
Scheduling Window (Days):	Up to 28 days before Start of priming phase	treatment day 1, before drug administration	At time of Discontinuation	30 days post discontinuation	Every 8 weeks post discontinuation	Every 12 weeks			
Laboratory Procedures/Assessments: analysis performed by LOCAL laboratory									
Pregnancy Test – Serum β-HCG		X		X					
PT/INR and aPTT		X	X	X	X	X	X		
CBC with Differential		X	X	X	X	X	X		
Comprehensive Serum Chemistry Panel		X	X	X	X	X	X		
Urinalysis		X							
T3, FT4 and TSH				X	Q6 weeks or when clinically indicated				
Efficacy Measurements									
Tumor Imaging		X	Q8 weeks	X	Q9 weeks	X		X	
Archival Tissue Collection/Tumor Biopsies/Correlative Studies									
Archival Tumor FFPE	X								
Tumor Biopsies (2)		X	at PD ^{3;4}	X		X			
Correlative Studies - Blood Collection		X ⁵	at PD	X	X	X			
Correlative Studies - Faeces Collection		X	at PD	X	X ⁶	X			

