Correlative Studies - Buccal Swabs Collection		X	at PD	X	X ⁶	X			
1: TMZ diary must be completed by patient and checked by the Investigator 2: tissue biopsies are not mandatory in MMR-D patients and might be performed at physician's discretion 3 : mandatory (MMR-P) 4 : within max. 7 days from imaging PD 5 : up to 28 days before TMZ administration on cycle 1, and then every 2 cycles 6 : at the 5th cycle of treatment 7 : Mandatory after the last dose of study treatment or before the initiation of a new anti-cancer treatment 8 : Participants who discontinue study treatment for a reason other than disease progression. Every 12-weeks after 1 year. Informations regarding disease status until the start of new anti-cancer therapy, disease progression, death, end of the study or if the participant begins retreatment with pembrolizumab (as detailed in Section 7.3.5).									

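### For cohort P patients dosed more than 28 days after the TMZ progression scan, section 9.1.3.1 requires a newer scan but still names the older one as the response baseline

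*Combined protocol and SAP*

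**What the plan says.** All references are to the combined protocol and SAP.

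- **Window (9.1.3.1, TRIAL phase):** "Tumor imaging must be performed within 0 to 28 days prior to starting treatment with pembrolizumab".
- **Cohort D baseline, listed under that rule:** "Baseline for D-cohort patient; Imaging data from Screening phase can be used, provided timeframe is less than 28 days".
- **Cohort P baseline, listed next:** "Baseline for P-cohort patients: the baseline correspond to the TMZ PD imaging assessment". No age condition is attached.
- **Time allowed before the TRIAL phase (4.1.2):** patients with a qualifying mutational load "will proceed to trial phase no longer than week 5 post TMZ-ML". The stated reason is the time needed to run and interpret the assay.
- **The same gap in 7.6.1:** palliative treatment may be "delivered for symptomatic disease during the 5-week gap between progression to TMZ and start of pembrolizumab treatment". This sentence refers back to 4.1.2.
- **Biopsy timing (8.0, footnote 4):** the biopsy at progression is to be taken "within max. 7 days from imaging PD".
- **Entry criterion 7 (7.1.3):** imaging within 28 days, counted to enrolment and not to first dose, for both cohorts.
- **Flow chart (8.0):** tumour imaging is marked in the column "Pembro Cycle 1 Day 1 Q3". Nothing there says that this scan becomes the response baseline.

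**The concern.** The primary endpoint is ORR to pembrolizumab in cohort P, so every response is a change from this baseline scan. When the first dose falls more than 28 days after the progression scan, two sentences of 9.1.3.1 point to different scans: one requires an in-window scan, the other names the out-of-window scan as baseline. A site that complies with the window then holds two candidate baselines, and the only one the text names is the older.

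If the older scan is used, more of the tumour change before the first dose is counted in the ORR attributed to pembrolizumab. That change may be growth. It may also be an effect of treatment given while the assay is awaited, since 4.1.2 says: "During the 5-week gap, standard palliative treatment with the exception of regorafenib, can be delivered, at physician discretion, for symptomatic disease control". How far that permission reaches is itself unclear. Exclusion criterion 3 (7.2) bars systemic anti-cancer therapy in the 4 weeks before enrolment. Section 7.6.1 allows palliative radiotherapy to non-target lesions, and 7.6.2 adds a symptomatic brain metastasis. Section 7.6.2 also cites an exception to its ban on antineoplastic therapy under numbers 5.1.2 and 8.2.1, which the current text does not contain.

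Under 10.3.2 the central reading prevails over the local one, so both need the same baseline. Section 9.1.3.1 mentions an imaging review protocol, but it is not part of these documents, so the central rule cannot be checked. The cohort is small: under 10.2, 0 versus 1 response in the first 10 patients decides whether stage 2 opens, and 4 versus 5 of 20 decides whether the null hypothesis is rejected.

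**Working it through.** The plan states no scan age or scan-to-dose interval to reproduce. The check is date arithmetic followed by an illustration.

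**Inputs.** Imaging limit 28 days (9.1.3.1). Gap of 5 weeks (7.6.1) or entry up to week 5 after the post-TMZ mutational load (4.1.2). Progression scan to biopsy, 0 to 7 days (8.0, footnote 4).

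**Step 1: age of the progression scan at first dose.** Age = (biopsy lag, where the gap runs from the biopsy) + gap. The rows assume that TRIAL entry means first dose.

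| Reading | Age (days) | Beyond 28 days |
|---|---|---|
| 7.6.1: 5 weeks from progression to dose | 5 × 7 = 35 | 7 |
| 4.1.2 from biopsy, first day of week 5 | 28 + 0 = 28 to 28 + 7 = 35 | 0 to 7 |
| 4.1.2 from biopsy, last day of week 5 | 35 + 0 = 35 to 35 + 7 = 42 | 7 to 14 |

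If the five weeks run from the assay result, or only to enrolment, the age could exceed 42 days. The documents give no figure for that. In 4.1.2 the five weeks are a maximum, so these are permitted ages and not expected ones.

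**Step 2: when the rules agree.** The progression scan stays in the window if biopsy to first dose takes at most 28 − 0 = 28 days (biopsy on the scan day) or 28 − 7 = 21 days (biopsy at day 7). Section 4.1.2, read to the end of week 5, allows 35.

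**Step 3: what an older baseline could do (illustration only).** Three assumptions come from outside the plan's text: partial response is a 30% fall in the sum of diameters, the sum changes by a fraction g between the progression scan and first dose, and the rate of change is constant. The fall needed from the size at first dose is 1 − 0.7/(1 + g). With a 28-day-old scan replacing one of age A, it is 1 − 0.7/(1 + g)^(28/A).

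| | g = +10% | g = −10% |
|---|---|---|
| Progression scan as baseline | 1 − 0.7/1.1 = 36.4% | 1 − 0.7/0.9 = 22.2% |
| 28-day scan replaces a 42-day one | 1 − 0.7/1.1^(28/42) = 34.3% | 1 − 0.7/0.9^(28/42) = 24.9% |
| 28-day scan replaces a 35-day one | 1 − 0.7/1.1^(28/35) = 35.1% | 1 − 0.7/0.9^(28/35) = 23.8% |
| Scan on the dosing day | 30% | 30% |

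A 28-day-old scan is the oldest replacement the window allows. In that case the shift in the required fall is 36.36 − 34.31 = 2.1 or 36.36 − 35.14 = 1.2 points under growth, and 24.91 − 22.22 = 2.7 or 23.84 − 22.22 = 1.6 points under shrinkage. A later scan within the window removes more.

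**The case against.** The strongest reply is that the cohort P line sits under the 0 to 28 day sentence: the parent sets the age and the line below only names the scan. Entry criterion 7 adds a second 28-day limit, to enrolment. On that reading, a 35-day-old scan with no newer one is a protocol deviation and not something the plan permits. This stands in part. A reader might infer that cohort P has no age limit at all, and the documents do not support that. But the reply does not settle which scan is the baseline once the newer one has been taken.

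Further points stand:

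- A reader might take 7.6.1 as showing that every cohort P patient waits 35 days. It refers back to 4.1.2, which sets a maximum.
- The flow chart marks imaging at pembrolizumab cycle 1, and its scheduling row appears to place assessments on treatment day 1 before dosing. That suggests a fresh scan, but no sentence makes it the baseline.
- A reader might infer that tumour-shrinking treatment is freely allowed in the gap. Exclusion criterion 3 and the radiotherapy limits point the other way, and the passages do not fit together clearly.
- Some pre-dose change is counted even with a compliant 28-day-old scan, and in the illustration the least favourable compliant scan moves the required fall by less than 3 points.
- The sensitivity of the decision rules to one patient applies to any misclassification. It is not evidence that one occurs here.
- A mismatch between local and central baselines is possible but not shown.

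**Conclusion.** The point holds for a defined group: cohort P patients whose first pembrolizumab dose comes more than 28 days after the TMZ progression scan. For them 9.1.3.1 requires an in-window scan and still names an out-of-window scan as the baseline for the primary ORR. The excess is 7 days on the wording of 7.6.1. It is 0 to 14 days when the five weeks run from the biopsy, depending on the biopsy lag and on how week 5 is counted, and possibly more on other readings. The documents do not say how many patients this will affect.

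It would go too far to conclude that ORR is biased in a known direction or by a known amount. Growth before dosing makes a response harder to reach and shrinkage makes it easier, and the plan gives no data on either. The 10% changes above are assumptions, and 42 days is not a firm upper bound. This is an inconsistency in the primary-endpoint baseline that should be corrected. It is not evidence that the result would be invalid.

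**What to change.** In 9.1.3.1, state that the cohort P response baseline is the most recent scan within the already required 0 to 28 days before the first pembrolizumab dose. The TMZ progression scan serves as baseline only if it falls in that window; otherwise it documents progression for eligibility only. In the flow chart, tie the cycle 1 imaging mark to this scan. Apply the same rule in local and central reading, and record the interval from baseline scan to first dose.

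Reconcile the timing statements in 4.1.2, 7.1.3 (criterion 7), 7.6.1, 8.0 (with footnote 4) and 9.1.3.1, including the event from which the five weeks run and whether they end at enrolment or first dose. Separately, reconcile the palliative-treatment sentence in 4.1.2 with exclusion criterion 3 and with 7.6.1 and 7.6.2, including the cross-references in 7.6.2.

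The cost is wording changes, one recorded interval, and a repeat scan only where 9.1.3.1 already requires one. Change between an in-window scan and the first dose will still be counted; the fix limits it to at most 28 days.
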